## 6.0 Data and Specimen Banking

### 6.1 Data management:

- **Storage and Access:** Data collection is the responsibility of the clinical research staff under the supervision of Drs. [name] and [name]. Study data will be recorded within a RedCAP database with study personnel being granted access to the database based on the tasks listed in the Delegation of Authority log. Only deidentified data with no PHI will be exported for analysis. The electronic consent (eConsent) forms, which will be maintained in a University of Minnesota RedCap database with established functionality for this purpose in our group. The database is HIPAA compliant.
- **Monitoring:** A designated study monitor will review 100% of electronic consent documents, study drug administration data, and SAE reporting. Additionally, a random sampling of 5% of subjects will undergo full evaluation and comparison of source documentation with data entered into the study database. The first data monitoring visit will be scheduled once 10% of the cohort has been enrolled, with repeat monitoring after 50% and 100% of enrollments. Monitors will evaluate 100% of users to ensure assigned access is consistent with training and delegation of authority logs. Remote clinical monitoring with source verification of the electronic health record will be allowed given limitations in local site access in the setting of the COVID epidemic limiting in person monitoring consistent with risk-based monitoring principles.
- **Release/Sharing:** Data will be shared among members of the study team with appropriate access assigned in Redcap based on study role, training, and delegation of authority. Data will be made available to assigned study monitors, the data safety monitoring board, the appropriate University of Minnesota oversight authorities, the Food and Drug Administration, and other state and federal regulatory authorities as required by state and federal law.
- **Data sharing:** Requests for data following study completion for sharing will be evaluated by a steering committee that will be established and will

include the principal investigators. Requests will be evaluated on a case-by-case basis. If data are shared, only deidentified data will be shared.

#### 6.2 *Biospecimen management:*

- **Specimen banking:** Biologic specimens (nasopharyngeal or oropharyngeal swabs and blood samples) provided by patients will be transported via courier service with the capacity to transport biologic materials with due consideration of communicable diseases. Specimens will be transported and processed by the University of Minnesota BSL-3 laboratory and frozen at -80 C until the time of analysis. Samples will be deidentified and labeled only with a patient ID number. Other sites will be encouraged to also obtain these specimens using local resources, with transfer of collected materials as they are able.
- **Biospecimens and protocol deviations:** Baseline clinical laboratory results will be required to establish inclusion and exclusion criteria, and missing data will be reported as protocol deviations. However, significant barriers exist to the collection and processing of other biospecimens due to the increased containment required, meaning that not every study site may be able to accomplish these procedures. In addition, patient self-collection will lead to missing samples. While every effort will be made to obtain these biospecimens, failure to do so will not constitute protocol deviations.
- **Specimen sharing:** Requests for specimen sharing during or following study completion for sharing will be evaluated by a steering committee that will be established and will include the principal investigators. Requests will be evaluated on a case-by-case basis. If specimens are shared, human genetic analysis will only proceed on those patients who opt-in to genetic testing. Genetic testing of viral genomes will be allowed to proceed on all patients.

### 7.0 **Sharing of Results with Participants**

7.1 *Sharing of results:* Data collected within this study will be obtained from the participants themselves and recorded on collection templates or directly into Redcap, or will be obtained from the electronic medical record and thus are already available to the patient and treatment team. Any testing of biospecimens will occur at a later time point and do have specific clinical relevance and will not be shared with the patient.

#### 7.2 *Sharing of genetic testing*

- **Disclosure of results:** There is no plan to disclose genetic results to the patients as none is yet planned.
- **If returning results to participants:** N/A

7.3 *Future analysis of genotypes:* Genetic testing, while potentially an area of future investigation as a means to determine if participants with specific genetic differences are more or less susceptible to COVID-19, is not currently planned nor funded. As such, data will not be disclosed to the participants. To the extent possible in future work, participants or families with rare variants will undergo attempts at anonymization.

## 8.0 Study Population

### 8.1 *Inclusion Criteria*

- Presumptive positive laboratory test for Covid-19 based on local laboratory standard
- Age greater than or equal to 18 years of age
- Admission to the hospital with a respiratory SOFA  $\geq 1$  and increased oxygen requirement compared to baseline among those on home O2
- Randomization within 48 hours of presentation of hospital admission or within 48 hours of a positive test result, whichever is later

8.2 *Rationale for inclusion criteria:* This is a pragmatic trial looking to enroll a diverse cohort of participants so the results may be broadly applicable to a wide patient population if efficacious. We do not have sufficient data to support lack of efficacy in a specific subgroup at this time to justify their exclusion. However, a respiratory SOFA of at least 1 is included to provide room for improvement to meet the primary efficacy endpoint. Patients on home oxygen therapy must demonstrate an acute deterioration under the same rationale. While we currently propose to exclude children due to insufficient time at the writing of this protocol to closely scrutinize safety and dosing in that group, along with logistical challenges of having different doses, we have plans to evaluate the possibility of expanding to include that patient population as soon as logistically feasible.

### 8.3 *Exclusion Criteria*

- Randomization  $> 48$  hours of admission order or positive test result, whichever is later
- Currently taking an angiotensin converting enzyme inhibitor (ACEi) or Angiotensin receptor blocker (ARB)
- Prior reaction or intolerance to an ARB or ACE inhibitor, including but not limited to angioedema
- Pregnant or breastfeeding women
- Lack of negative urine or serum pregnancy test
- Not currently taking a protocol allowed version of contraception: intrauterine device, Depo-formulation of hormonal contraception (e.g. medroxyprogesterone acetate / Depo-Provera), subcutaneous contraceptive (e.g. Nexplanon), daily oral contraceptives with verbalized commitment to taking daily throughout the study period; use of condoms or agree to abstain from sexual intercourse during the study. All women of child bearing age enrolled in this fashion will be informed of the teratogenic risks. If enrolled under LAR, they will be informed of the risks after regaining capacity.
- Patient reported history or electronic medical record history of kidney disease, defined as:
  - Any history of dialysis
  - History of chronic kidney disease stage IV

- Estimated Glomerular Filtration Rate (eGFR) of < 30ml/min/1.73 m^2 at the time of randomization
- Severe dehydration at the time of enrollment in the opinion of the investigator or bedside clinician
- Most recent mean arterial blood pressure prior to enrollment <65 mmHg
- Patient reported history or electronic medical record history of severe liver disease, defined as:
  - Cirrhosis
  - History of hepatitis B or C
  - Documented AST or ALT > 3 times the upper limit of normal measured within 24 hours prior to randomization
- Potassium >5.0 within 24 hours prior to randomization *unless* a repeat value was <=5.0
- Treatment with aliskiren
- Inability to obtain informed consent from participant or legally authorized representative
- Enrollment in another blinded randomized clinical trial for COVID

8.4 *Rationale for exclusion criteria:* We expect treatment results to be available within 24 hours of testing given the acuity of the patient, though delays are expected so this window is open until 48 hours for logistical considerations. We wish to limit interventions to an early window, as progression from admission to mechanical ventilatory support occurs within days, and we intend to maximize potential efficacy of the treatment to mitigate respiratory failure. Patients already taking or with prior adverse events to either an ACE inhibitor or ARB are excluded for risk of side effects. Losartan is a class D drug. Women of child bearing age (14-60) without a history of hysterectomy must have a documented negative pregnancy test in the emergency department or have had a prior history of hysterectomy. We will exclude patients with significantly elevated creatinine or liver enzymes expected to affect drug clearance. Aliskiren is contraindicated for losartan co-treatment. Patients with hypotension will be excluded given an expected decrease of 6-8 mmHg in their blood pressure that might necessitate the need for cardiovascular interventions. Finally, all patients or their legally authorized representative will give written informed consent.

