molecular docking analysis of the coronavirus macrodomain. We propose a dose increase to 100 mg daily (50 mg PO BID in patients without renal dysfunction). We have previously utilized this dose in previous RCTs in HIV ([name]/[name]). These studies confirmed the safety profile of Losartan with a mean systolic blood pressure (SBP) reduction of only 7 mmHg at 100 mg daily and excellent tolerability and safety profile. Our findings confirm prior reports of 6 mmHg mean SBP reduction for Losartan when doses at 100mg daily. Patients will receive intensive safety monitoring as this will be delivered in the inpatient setting with blood pressure checks multiple times per day and minimum required potassium, creatinine and GFR checks prior to enrollment, day 1, 3, and 7 (or prior to discharge). In addition, patients will have routine creatinine and potassium monitored if ordered clinically. We hypothesize significant benefit as 4 preliminary and observational reports out of China and the UK suggest significant reductions in disease severity and inflammatory profile for patients treated with ACEi or ARBS with no preliminary reports suggesting harm from ACEi or ARBS in Covid19 patients.

- We propose a dose of 50 mg twice daily, given significantly improved RAS blockade. This is a higher dose than we are proposing for study in outpatients, as patients will be carefully monitored with regular blood pressures and renal function testing. Furthermore, patients will have a higher severity of illness and are more likely to benefit from more robust blockade. Patients with moderate renal dysfunction (eGFR 30-59 mL/min/1.73 m^2) will be given 50 mg once daily given impaired renal clearance.

4.2 *Placebo arm:* The same volume of suspension prepared according to the package insert will be administered without the active ingredient. Any unused doses of placebo will be discarded if unused by the 28 day time point.

4.3 *Investigational new drug:* The study will be conducted under IND 148365.

4.4 *Timing of the intervention:* Treatment will continue for 10 days or hospital discharge.

4.5 *Duration of study participation:* The final follow-up will occur at 90 days after randomization to determine episodes of delayed hospitalization. Data analysis is expected to be completed within 1 year of enrollment of the final patient.

4.6 *Drug Handling, blinding, and randomization:*

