stroke. While the rationale for eConsent is different in this case (minimization of disease spread during a pandemic), we believe it is appropriate for the disease and intervention being studied. Critically, the established safety profile of losartan, with minimal side effects of effects on blood pressure in healthy patients without an overactive renin-angiotension-aldosertone system, combined with the close telemedicine and EMR based follow-up methods proposed in this study make the risk : benefit ratio for the alteration of traditional consent process acceptable for participants, providers, and the public.

5.3 *Administration of study drug:* Study drug will be dispensed to bedside nurses twice daily for administration. Patients unable to take the suspension (due to endotracheal intubation) will have it administered via an orogastric or nasogastric tube, or G-tube. If the patient is unable to receive the study drug for respiratory distress, we will allow for +/- 3 hours from the scheduled time of drug administration. If this is not possible, the patient will not receive that dose, and this will be tracked.

5.4 *Patient follow-up:* Participants will receive remote telemedicine, phone, or in person evaluation by trained study personnel every day for the 10 days of the intervention period to monitor for the development of complications as well as day 15. In addition, electronic medical record labs and notes will be monitoring for the development of AE and SAEs. Data will be documented into a Redcap database. The coordinators will have patients complete 2 surveys at enrollment, day 4, day 10, and day 28 (both attached in supplement), if the patient can cooperate. If not, the reason for failure to complete the survey will be recorded. Surveys conducted within 1 day of the time point will be counted as qualifying and not missing. Patients will be contacted at day 28 (+/3 days) and 90 (+/- 3 days) for intermediate term outcomes. If follow-up procedures are not completed due to inability (patient unavailable or intubated), or due to loss to follow-up, these will not be counted as protocol deviations.

5.5 *Pharmacokinetics:* Patients undergoing this voluntary substudy will have up to another 9 mL of total blood drawn (30 mL total day 1 instead of 21-24 mL day 1. The remainder of the samples will be the same for the duration of the study). Blood will be processed, frozen at -80 C until shipping to [name] at the University of Nebraska for analysis.

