## **13.0 Risks to Participants**

*13.1 Foreseeable Risks:* Potential risks of losartan are detailed in consent forms. The most severe risks of losartan use include teratogenicity in the setting of pregnancy, hypersensitivity including angioedema, symptomatic hypotension, worsening of renal function, and electrolyte abnormalities. The most common side effects of losartan include fatigue, weakness, diarrhea, chest pain and anemia. Subjects will be rigorously screened to ensure that they are at low risk for complications due to losartan and they will be monitored closely for side effects and signs of toxicity. The package insert for Losartan has been included with this protocol. Clinical trial and post-marketing surveillance data (see package insert) demonstrate an

excellent safety profile. In over 4,000 patients, there was a low incidence of adverse events (2.3%) comparable to placebo (3.7%). The effects more common in losartan than placebo were clinically minor, including dizziness (3% vs 2%), upper respiratory infection (8% vs 7%), nasal congestion (2% vs 1%) and back pain (2% vs 1%). While losartan has the potential to cause symptomatic hypotension, four studies have identified losartan has a negligible effect on resting blood pressure and heart rate in healthy volunteers. While there may be a higher risk in critically ill patients, we will exclude patients with bedside clinician assessment of volume depletion that might increase the risk of side effects. It has been theorized there may be an increase risk of cardiac dysfunction in patients taking an ACE-I or ARB in COVID-19, though evidence for this effect is lacking. We will monitor troponin and BNP/pro-BNP levels in participants and report these data to the DSMB if measured clinically. In fact, the most recent preprinted (non-peer reviewed) data from China now suggest a protective effect based on retrospective data compared to other antihypertensive regimens. Nevertheless, based on this recent suggestion, we will track troponin and BNP/proBNP measurements in addition to our previously planned assessments of new episodes of hypotension and shock, and report these data to the DSMB. In addition, all patients are closely monitored for clinical purposes given their severity of illness, combined with daily assessments for AEs and SAEs will allow for early detection of side effects and reduce the risks to patients.

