- **Response to possibly, probably, or definitely related AEs and SAEs:** SAEs determined to be probably or definitely related will prompt discontinuation of study drug. AEs determined to be probably or definitely related with prompt a) decrease in study drug from twice a day to once a day if currently dosing twice daily, b) discontinuation of study drug if only taking once daily, or c) discontinuation for study drug at the discretion of the investigator.
- **Anticipated Adverse Events:** Adverse events are not expected from any of the study procedures. We do not expect any serious adverse events due to losartan.
- **Recording and Documentation**
  - At each contact with the subject, personnel must seek information as to discomforts or adverse experiences by specific questioning and, as appropriate, by examination. This will typically occur via phone or telemedicine due to concerns regarding infectious contagion. Information about AEs to be recorded includes event description, time of onset, investigator assessment of severity, relationship to Study Agent(s)/Intervention(s), and time of resolution/stabilization of the event. All AEs occurring during the study period (from time of consent signing to study day 15) must be documented appropriately regardless of relationship to study products or procedures unless included on the list of clinical outcomes that may be exempt from adverse outcomes reporting as part of the study protocol and outcomes. Information on all identified AEs will be recorded within 5 days of recognition in the appropriate AE module of the case report form (CRF) on Redcap, and within 24 hours in the event of a SAE.

18.3 **Data Safety Monitoring:** A data safety monitoring board (DSMB) has been convened and includes 4 individuals meeting the key element criteria below, and includes a biostatistician with prior clinical trials DSMB experience. The DSMB will follow the guidance as outlined in the application and the attached charter unless there is a compelling, unanticipated reason to deviate from these rules. Data regarding the primary outcome (hospitalization) will be reported to the DSMB continuously, consistent with continuous study monitoring principles. The DSMB may recommend stopping the trial early only for safety, following these guidelines:

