21.6 *Cognitively Impaired Adults, or adults with fluctuating or diminished capacity to consents:* To establish capacity in this setting, the MacArthur Competence Assessment tool will be administered by trained study personnel. If the patient lacks capacity, a LAR may provide consent for these participants on their behalf. For adults unable to consent, consent will be obtained from a legally authorized representative in the following order of priority consistent with Minnesota State Law: health care agent previously assigned via a health care power of attorney, spouse, parents, adult children, and then adult siblings. An incapacitated adult who has a court appointed guardian would require permission of the court for enrollment, and these participants will be excluded practically from the trial.

21.7 *Adults Unable to Consent:* The same process will be applied as in 21.6.

21.8 *Assent and dissent in adults with fluctuating or limited mental capacity:*

- **Assent:** If patients might have capacity, we use the MacArthur Competence Assessment Tool for Clinical Research. If they do not reach the pre-specified threshold for capacity, we seek from an LAR. We do not seek further assent, as these patients are frequently intubated, delirious, or medically sedated
- **Dissent:** However, even if the LAR consents to the trial, if the patient is awake and alert, but dissent, we will exclude the patient.

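### The blood-pressure exclusion in 8.3 looks only at the latest MAP, so a patient whose MAP is kept at or above 65 mmHg by a vasopressor can be enrolled, which falls short of the purpose given in 8.4

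*Combined protocol and SAP*

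**What the plan says.** Section 8.3 contains one numeric blood-pressure exclusion: "Most recent mean arterial blood pressure prior to enrollment <65 mmHg". The only other exclusion with a direct bearing on circulation is severe dehydration, judged clinically. Section 8.1 sets a floor on respiratory severity (respiratory SOFA of at least 1) and no ceiling.

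Section 8.4 gives the reason for the blood-pressure rule: "Patients with hypotension will be excluded given an expected decrease of 6-8 mmHg in their blood pressure", with the concern that the fall could call for cardiovascular intervention. Section 4.1 gives the supporting experience as a "mean systolic blood pressure (SBP) reduction of only 7 mmHg at 100 mg daily", and cites earlier reports of a 6 mmHg mean systolic fall at the same dose.

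Section 13.1 accepts that the critically ill may be more exposed and answers with an exclusion for volume status: "While there may be a higher risk in critically ill patients, we will exclude patients with bedside clinician assessment of volume depletion". Elsewhere the protocol treats vasopressors as a response to hypotension: 3.3 counts them as an intervention for a hypotensive episode, and 18.3 names their initiation as one of two SAEs of interest.

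**The concern.** A MAP reading means something different when a drug is holding it up. A patient at MAP 66 mmHg on a vasopressor might be below 65 mmHg without it, and so might have met the exclusion. The event that 8.4 wants to avoid, a cardiovascular intervention for low pressure, has already happened in that patient. The 8.3 rule does not see this because it takes the number alone.

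The stake is patient safety in a group with little reserve for a further fall in pressure, half of whom would be allocated to losartan under 1:1 randomization. There is a smaller cost to monitoring: vasopressor initiation cannot register as a new event while a patient is already on one, although need for vasoactive drugs still goes to the DSMB under 18.2. The primary endpoint and its analysis are not at issue.

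**Working it through.** The plan gives no figure for this point, so the check is mainly a reading of the criteria against their rationale.

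**1. Who passes the rule.** Crossing the latest MAP with vasopressor use gives four cases:

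| Latest MAP | Vasopressor | Result under 8.3 |
|---|---|---|
| <65 mmHg | no | excluded |
| <65 mmHg | yes | excluded |
| ≥65 mmHg | no | eligible |
| ≥65 mmHg | yes | eligible |

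The fourth row is the gap. Nothing in 8.1 or elsewhere in 8.3 closes it.

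**2. Whether another provision closes it.**
- Dehydration (8.3) and volume depletion (13.1) concern volume. A volume-replete patient on a vasopressor meets neither.
- Treating-physician agreement before approach (5.1) may keep some of these patients out, but it is discretionary.
- Repeated blood-pressure checks (4.1), dose reduction or stopping (18.2) and DSMB review (18.3) act after dosing. The stopping rule also rests on investigator attribution: "SAEs determined to be probably or definitely related will prompt discontinuation of study drug".

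**3. Whether such patients can reach enrollment.** The support is indirect. On consent for patients who lack capacity, 21.8 says "these patients are frequently intubated, delirious, or medically sedated". Section 5.3 provides for tube dosing: "Patients unable to take the suspension (due to endotracheal intubation) will have it administered via an orogastric or nasogastric tube", but that also serves patients intubated after entry. Neither section mentions vasopressors, so intubation is only a proxy. Transfers are eligible (1.5), and the 48-hour window can run from a positive test instead of admission (8.1).

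**4. Size of the fall (illustrative).** 8.4 does not say which pressure falls by 6-8 mmHg; the figures in 4.1 are systolic. With MAP = (SBP + 2 × DBP)/3, a fall in systolic pressure alone lowers MAP by one third: 6/3 = 2.0 and 8/3 = 2.7 mmHg.
- From MAP 66, if MAP itself falls: 66 − 6 = 60 and 66 − 8 = 58.
- From MAP 66, if only systolic falls: 66 − 2.0 = 64.0 and 66 − 2.7 = 63.3.
- Starting MAP needed to stay at or above 65: 65 + 6 = 71 to 65 + 8 = 73 if MAP falls; 65 + 2.0 = 67.0 to 65 + 2.7 = 67.7 if only systolic falls.

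The crossing below 65 therefore occurs only near the cut-off, and it is the same for a patient without a vasopressor. This arithmetic describes the margin; it does not separate supported from unsupported patients.

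**5. Number affected (illustrative).** Let e be the share on a vasopressor at entry, which is assumed because the documents give none. With 200 participants and 1:1 allocation:

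| e | 200 × e | on losartan | 200/(1 − e) |
|---|---|---|---|
| 2% | 4 | 2 | 204.1 |
| 5% | 10 | 5 | 210.5 |
| 10% | 20 | 10 | 222.2 |

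The last column is the number of patients meeting today's criteria that would be needed to randomize 200 under the extended rule.

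**The case against.** The strongest defence is that 8.3 agrees with the protocol's own definition: 3.3 also sets hypotension at MAP below 65 mmHg, so the rule and the definition match. That stands as far as it goes. Extending the rule is a tightening toward the aim in 8.4, and the protocol does not contradict itself on the threshold. But 3.3 also lists vasopressors as an intervention for hypotension, so treated hypotension falls within the concern that 8.4 describes.

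The second defence is that few such patients will present. The trial stresses early treatment, enrolls in the emergency department or designated COVID-19 areas, and cites 2-3 days from hospitalization to ventilation. This also stands: the number is unknown and probably small.

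The third is that 8.2 wants a broad, pragmatic population. That section argues from the lack of evidence of inefficacy in any subgroup, whereas this exclusion concerns safety, on which 8.4 has already chosen to exclude hypotensive patients.

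Three stronger readings are tempting:
- A reader might infer that losartan would push supported patients below 65 mmHg. The arithmetic shows this only close to the cut-off and equally for unsupported patients. Section 13.1 reports a negligible effect on resting pressure in healthy volunteers, while allowing for more risk in critical illness.
- A reader might infer that nothing objective protects these patients before the first dose. The MAP rule is objective, acts before dosing, and does exclude patients on a vasopressor whose MAP is still below 65.
- A reader might add that no hold rule exists for low pressure, since the missed-dose rule in 5.3 concerns respiratory distress: "If the patient is unable to receive the study drug for respiratory distress, we will allow for +/- 3 hours". That is a separate question, and an entry criterion would not settle it.

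**Conclusion.** The concern holds in a limited form. As written, 8.3 admits patients whose MAP is at or above 65 mmHg because of a vasopressor, and this does not fully serve the purpose in 8.4. The conclusion rests on the text of 8.1, 8.3 and 8.4 alone and needs no numerical assumption. Its size cannot be estimated from the documents: the 2-10% shares and the MAP 66 example only illustrate scale. The documents do not support a claim that many patients would be exposed, or that the protocol sets out to enroll patients in shock. It is worth changing because it is a safety matter that is cheap to put right.

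**What to change.** In 8.3, extend the criterion to: most recent MAP <65 mmHg, or receiving a vasopressor for hypotension at enrollment. A matching clause in 8.4 would make the reason explicit.

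The cost is one line and no new data collection: vasopressor type and dose are already recorded (1.6), and a SOFA score is already scheduled at enrollment (5.6). Eligibility becomes slightly narrower, so recruitment may need a few more candidates. The planned minimum of 200 participants and the power calculation in 15.2 are unchanged.
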